3.0 Animal Studies and Previous Human Studies

Modalities that rely on NIRAF detection for label-free parathyroid identification have been successfully validated in several studies (15-18). FDA approval for this application was recently granted to Fluobeam (a commercially available imaging system) and PTeye (a commercial fiber probe-based system) in 2018 (14). Certain outcome studies have reported that imaging-based systems for NIRAF detection such as the PDE Neo II system was able to reduce the number of frozen sections (or PTH aspirate) required during parathyroid procedures (17). However, other studies have reported that they observed no benefit from imaging-based systems in parathyroid localization (19). In a recent study, Thomas *et al.* demonstrated that a fiber probe-based system – the PTeye – was more sensitive in parathyroid identification compared to the imaging-based system by PDE Neo II (20). To date, there has been no studies that determine the impact of a fiber probe-based system (i.e. PTeye) during parathyroid surgeries in minimizing a number of frozen sections (or PTH aspirate) obtained intraoperatively or postsurgical complications.

4.0 Inclusion/Exclusion Criteria

Inclusions:

- All adults (i.e., ≥ 18 years old) patients with primary hyperparathyroidism who will be undergoing parathyroid surgery
- All adults (i.e., ≥ 18 years old) patients with persistent primary hyperparathyroidism after having undergone a failed prior parathyroid surgery who will be undergoing repeat parathyroid surgery

Exclusion:

- Children and minors
- Pregnant women
- Patients with concurrent parathyroid and thyroid disease that require total thyroidectomy
- Patients with secondary or tertiary hyperparathyroidism

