5.0 Enrollment/Randomization

The research will be designed as a single center study, where patient recruitment will be conducted by the participating surgeon at UCSF. The initial evaluation will be conducted while the surgeon is evaluating the patients. The final eligibility of each patient for participating in this study will be determined by the participating surgeon in accordance of his/her medical conditions. Following the exclusion criteria, the study will aim to accrue all eligible patients who are going to the OR as part of their standard surgical procedure.

All participants must be provided a consent form describing the study with sufficient information for each participant to make an informed decision regarding their

participation. Participants must sign the IRB-approved informed consent form prior to participation in any study specific procedure. The participant must receive a copy of the signed and dated consent document. The original signed copy of the consent document must be retained in the medical record or research file.

1. On the date of procedure consent at clinic or the date of surgery, patients will be given a paper consent form detailing about the outcome study with PTeye in addition to the consent for the surgical procedure that will be performed.
2. The key study personnel will briefly describe the PTeye and its application to the patient.
3. If the patient is interested in participating, the key study personnel will provide the patient with a paper-based consent form.
4. The key study personnel or the surgeon assigned to the patient will be available to discuss the protocol with the patient (including, risks, benefits, alternatives, etc.). The patient will also be provided with the contact information of the principle investigator should they have any questions.
5. If the patient consents to be part of the study, a scan of their signed consent form will be stored digitally in the patient's medical record.

Prior to surgery, the patient will be assigned a unique ID (e.g. Para_001). The unique ID will be utilized for randomly allocating the patient to the experimental arm (where the surgeon will use PTeye) or a control arm (where the surgeon will not use PTeye). The allocation will be conducted by the study coordinator using 'Random Allocation Software' (<http://mahmoodsaghaei.tripod.com/Softwares/randalloc.html>).

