6.0 Study Procedures

For patients assigned to the study arm, the surgeon will use the PTeye as an intraoperative tool to identify if a suspect tissue is a parathyroid or not, during the parathyroid surgery. The surgeon will first take 5 baseline NIRAF measurements on the thyroid gland (or neck muscle, if thyroid is absent) using the disposable sterile fiber probe that is connected to the PTeye console (see Figure 1), as per device functionality requirements. The subsequent step would involve touching the target tissue in the neck with the fiber optic probe, following which the PTeye will indicate to the surgeon if the tissue is parathyroid or not. Parameters which are displayed on the PTeye console – Baseline values, Detection Intensity, Parathyroid Detection Ratio – will be recorded for each patient enrolled in the study arm. PTeye indicates that a tissue is parathyroid if it displays the 'Parathyroid Detection Ratio' is greater than 1.2. The rest of the surgical procedure will follow according to standard protocol.

For patients assigned to the control arm, the surgeon will not use the PTeye and will proceed with the parathyroid surgery as usual, while relying solely on her/his surgical experience in identifying the parathyroid glands during the operations.

Figure 1. A commercial fiber probe-based system (PTeye, [REDACTED]) for detecting near infrared autofluorescence (NIRAF) utilized for intraoperative parathyroid gland identification. PTeye consists of 1) the console that has a display and indicates to the surgeon if a tissue is parathyroid or not, 2) a detachable fiber optic probe, and 3) a foot-pedal which is activated by the surgeon for tissue NIRAF measurements.

De-identified information regarding (i) patient demographics, (ii) duration of surgery, (iii) number of frozen section (or PTH aspirate) analysis performed, (iv) frozen section (or PTH aspirate) and permanent histology reports of all excised tissues, (v) blood calcium levels (before surgery, 5-14 days after surgery and 6 months after surgery), (vi) parathyroid hormone (PTH) levels (5-14 days after surgery and 6 months after surgery) and (vii) postsurgical complications, if any and history of ER visits or hospitalization or repeat surgeries due to high or altered calcium levels, will be compiled for all enrolled patients. These parameters would then be compared between the study arm and the control arm to truly gauge the impact or value of a device like PTeye for parathyroid surgeries.

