10.0 Statistical Considerations

Currently there are no comparable published randomized trials that have evaluated the effect of NIRAF detection for reducing intraoperative frozen section analysis (or PTH aspirate) during parathyroidectomies. Based on preliminary data obtained from a similar ongoing study at Vanderbilt University Medical Center over 123 patients, an 83% reduction in frozen section analysis was observed in the interventional group of 63 patients where NIRAF was used, compared to the control group of 60 patients where NIRAF was not used (unpublished). The mean frozen section analysis (FSA) obtained for the NIRAF group is 0.1 FSA/patient versus 0.6 FSA/patient obtained in the control group. Assuming, that an expected mean difference of 0.6 FSA/patient needs to be observed between the NIRAF and the control group, where the standard deviation of the enrolled study population is 0.8 (Standard Deviation obtained in VUMC study population is 0.78 FSA/patient), 47 patients would be required per group (for a 95% powered study). Since this study may involve patient follow-up for data up to 6 months after surgery, we will thus assume an approximate data attrition rate of 15%, thus requiring a recruitment of 55 patients per group. Therefore, a total of 110 patients (study and control arm) should be recruited per surgeon for this study at this study site. Overall, 110

patients need to be enrolled at this study site under a single surgeon to assess the impact of this technology.

Sample size	
2-side significance level	0.05
Power (1-beta)	0.95
Ratio of sample size, Control/NIRAF group	1
Expected mean in NIRAF group	0.7
Expected mean in Control group	0.1
Study population standard deviation	0.8
Result	
Sample Size - Control group	47
Sample Size - NIRAF group	47
Sample Size – Control group compensated for 15% attrition	55
Sample Size – NIRAF group compensated for 15% attrition	55
Total sample size	110

Analysis Plan:

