Continuous variables will be reported using medians and interquartile ranges (IQRs). Categorical variables will be reported using counts, percentages, and their 95% confidence intervals (CIs). Comparisons of the NIRAF and control parathyroidectomy groups for primary and secondary outcomes will be done using (a) 1-sided χ^2 or Fisher tests for categorical variables and (b) 2-tailed Student's t-test or Wilcoxon's test for continuous variables (depending on distribution of data). To analyze factors that influence the primary outcome assessed for this study, i.e., number of frozen sections specimens (or PTH aspirate) sent for analysis, a generalized linear mixed models will be used. The following variables will be considered as fixed effects for the study model: (i) nature of the intervention (NIRAF or control), (ii) age, (iii) BMI, (iv) number of intraoperative PTH assays, (v) number of diseased parathyroid glands seen, and (vi) type of parathyroid surgery (focused parathyroidectomy or bilateral neck exploration). The multivariate analysis based on this model will generate the respective odds ratios and their 95% CIs for the aforementioned factors that are being considered. A p-value ≤ 0.05 based on the statistical analysis for continuous/categorical variables under the primary and secondary outcomes measured in this study will be considered as significant.

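### First-versus-repeat operation is known before randomisation but is neither a stratum nor a model term, which costs some precision and leaves the primary estimate open to chance imbalance.

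*Combined protocol and SAP*

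**What the plan says.** Section 4.0 has two inclusion categories. One is adults with primary hyperparathyroidism having parathyroid surgery. The other is adult "patients with persistent primary hyperparathyroidism after having undergone a failed prior parathyroid surgery who will be undergoing repeat parathyroid surgery". No cap or expected share is given for the second.

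Section 5.0 describes allocation in one step: "The unique ID will be utilized for randomly allocating the patient to the experimental arm" or to control, using allocation software. It mentions no stratum, block or minimisation factor.

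The analysis plan in Section 10.0 compares the arms with a "2-tailed Student's t-test or Wilcoxon's test for continuous variables", without adjustment. It adds a generalized linear mixed model for the primary outcome. Besides the intervention, the fixed effects are "ii) age, (iii) BMI, (iv) number of intraoperative PTH assays, (v) number of diseased parathyroid glands seen" and "type of parathyroid surgery (focused parathyroidectomy or bilateral neck exploration". Previous parathyroid surgery is not among them, and no subgroup or sensitivity analysis by previous surgery is planned.

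**The concern.** The primary outcome counts specimens sent to confirm possible parathyroid tissue. Section 1.0 says such specimens are sent when the surgeon is in doubt, and it links failed operations to glands that could not be found. Reoperated patients are those in whom an operation has already failed. It is therefore plausible that they differ in specimen count, though the documents do not say so.

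The listed covariates do not fill the gap. Focused versus bilateral surgery describes extent, not whether the operation is a repeat, and the plan does not say whether it means planned or performed surgery. PTH assays and diseased glands seen are measured after randomisation, and the assay count is itself a secondary outcome.

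At stake is precision. There is also the awkward position of finding, once data are in, that a handful of reoperations fell mostly in one arm with no prespecified adjustment for it.

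**Working it through.** **Inputs from Section 10.0.** Planned difference 0.6 frozen sections per patient; pilot means 0.1 and 0.6, so a pilot difference of 0.5; SD 0.8; two-sided alpha 0.05; power 95%; 47 per arm, raised to 55 (110 in total).

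**Assumptions, not in the documents.** Reoperation share 10%, with 5% to 20% as the range; 0.5, 1 or 2 extra specimens per reoperation. The 5–10% in Section 1.0 is a failure rate for parathyroidectomy, not the enrolled share.

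**1. The plan's own figure.** n per arm = 2 × [(1.960 + 1.645) × 0.8 / 0.6]² = 46.2, so 47. This reproduces. For attrition, 47 × 1.15 = 54.05, which rounds up to the stated 55 (47 / 0.85 = 55.3 would round up to 56).

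**2. Standard error at 55 per arm.** 0.8 × √(2/55) = 0.153. The smallest significant difference is about 1.96 × 0.153 = 0.30.

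**3. Chance of imbalance.** With 11 reoperations among 110 and 55 per arm, the hypergeometric distribution gives P(arms differ by 5 or more, that is 8:3 or worse) = 0.202, so about 0.10 in each direction. With simple randomisation, binomial(11, 0.5) gives 0.227. The SD of the difference in counts is about 3.2 patients. At other shares:
- 5% (6 patients): a difference of 4 or more has probability 0.206.
- 15% (16 patients): a difference of 6 or more, 0.175.
- 20% (22 patients): a difference of 6 or more, 0.233.

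**4. Size of the shift.** Shift = difference in reoperation counts × extra specimens / 55. For a difference of 5, with power taken as Φ((d − shift)/0.153 − 1.96) when the imbalance works against the device:

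| Extra specimens | Shift | In SE | % of 0.6 | Power at d = 0.6 | Power at d = 0.5 |
|---|---|---|---|---|---|
| none | 0 | 0 | 0 | 97.6% | 90.6% |
| 0.5 | 5 × 0.5/55 = 0.045 | 0.3 | 8% | 95.3% | 84.6% |
| 1 | 5 × 1/55 = 0.091 | 0.6 | 15% | 91.6% | 76.5% |
| 2 | 5 × 2/55 = 0.182 | 1.2 | 30% | 78.3% | 55.0% |

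These powers keep the SD at 0.8 and apply only to trials in which that imbalance has occurred.

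**5. Type I error.** A Poisson simulation of the unadjusted t-test (20,000 trials per scenario) gave 0.047 to 0.051 overall in every scenario. Given an imbalance of 4 at 47 per arm, the conditional value is about 0.05–0.07 for 0.5 to 1 extra specimen and 0.08–0.13 for 2.

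**6. What adjustment gains.** Holding the total SD at 0.8, the variance explained at a 10% share is 0.1 × 0.9 × (extra specimens)². For 0.5 and 1 this is 0.0225 and 0.09 out of 0.64, or 3.5% and 14%. The n needed for 95% power falls from 47 to 45 and 40 per arm. Over shares of 5% to 20% it falls to 44–46 (0.5 extra) or 35–43 (1 extra).

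**The case against.** The strongest reply is that unstratified randomisation with an unadjusted test is a valid design, and that chance imbalance is already counted in the planned error rate. That stands. A reader might infer that an uneven split would produce a false device effect, or that the primary comparison is biased. The documents do not support this: overall type I error is preserved, and the exposure exists only conditionally, once an imbalance has occurred.

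The sizes also rest on two assumptions. One or two extra specimens is large beside a pilot control mean of 0.6; it would put a reoperation at (0.6 + 1)/0.6 = 2.7 to (0.6 + 2)/0.6 = 4.3 times that mean. A difference of 5 patients is beyond the typical 3.2. With 0.5 extra specimens the effect is minor. This stands too, and is why the full range is shown.

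Focused-versus-bilateral surgery and diseased glands seen may absorb some of the difference. They might, but neither is a clean baseline measure of previous surgery.

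Two further readings should be avoided. The Section 6.0 instruction for an absent thyroid concerns the thyroid, not a failed parathyroid operation, and is no evidence on this point. Nor would showing the secondary outcomes separately for reoperations help: at a 10% share there would be about 5 or 6 such patients per arm.

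**Conclusion.** The omission is confirmed from Sections 4.0, 5.0 and 10.0. A likely prognostic factor, known before allocation for every patient, is used in neither the randomisation nor the model. The consequence is modest: some lost precision, and about a one-in-five chance (at an assumed 10% share) of an imbalance that moves the estimate by 0.3 to 1.2 standard errors, depending on the assumed excess. It becomes material to the primary conclusion only if a reoperation adds about 2 specimens and the true difference is nearer the pilot's 0.5 than the planned 0.6. That previous surgery affects specimen count is itself a plausible assumption. The planned test remains valid, and the stated sample size need not rise on this account.

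**What to change.** In the Section 10.0 analysis plan, add first-versus-repeat parathyroid operation as a prespecified fixed effect in the primary-outcome model, and report the adjusted arm difference alongside the unadjusted test. Because the plan has that model yielding odds ratios, state that the adjusted difference will be given in specimens per patient, so that the two results can be compared.

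The cost is one degree of freedom and one data field that eligibility screening already establishes. No more patients are needed, and the change can still be made after enrolment has begun, provided it is fixed before outcomes are compared by arm.

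Stratified allocation in Section 5.0 is optional. With perhaps 5 to 16 reoperations (shares of 5% to 15%) and a single surgeon who learns each allocation, a separate list in fixed blocks would become partly predictable. It should be used only with block sizes that are varied and concealed.

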2.0 Rationale and Specific Aims

The goal of this study is to assess whether using PTeye – a NIRAF detection modality – can reduce healthcare associated costs after parathyroid surgeries and improve patient outcomes. The specific aims of this study is to determine if PTeye is beneficial or not for (i) intraoperative identification of parathyroid tissues, (ii) improving efficiency of parathyroid surgeries, and (iii) minimizing risk of postsurgical complications.

By being able to quickly and definitively locate parathyroid glands while in the operating room, the duration of surgical procedure could be further reduced. In addition, the number of frozen section biopsy (or PTH aspirate) and associated costs can be minimized. Furthermore, repeat surgeries as a result of missing a diseased parathyroid gland at the time of the initial parathyroidectomy for hyperparathyroidism could potentially be avoided.

Primary Outcome Measure:

1. Number of frozen sections (or PTH aspirate) sent for analysis
 - a. Number of frozen sections (or PTH aspirate) sent for analysis during the procedure to confirm potential parathyroid tissue [Time Frame: Immediate. During PTx procedure.]

Secondary Outcome Measure:

1. Persistent hyperparathyroidism (Immediate)

- a. Failure of intra-operative parathyroid hormone (PTH) to normalize (defined as failure of PTH to drop > 50% of its baseline value at final intra-operative PTH assay and/or failure of PTH to drop < 65 pg/ml or 6.9 pmol/L). [Time Frame: During parathyroidectomy (PTx) procedure]
- 2. Persistent hyperparathyroidism or hypercalcemia (transient)
 - a. Elevated blood calcium levels (total blood calcium level > 10.5 mg/dL or 2.6 mmol/L) with/without elevated parathyroid hormone (PTH) (serum intact PTH > 65 pg/ml or 6.9 pmol/L) at first postoperative visit. [Time Frame: 5-14 days after PTx procedure]
- 3. Persistent hyperparathyroidism or hypercalcemia (failed parathyroidectomy)
 - a. If blood calcium with/without parathyroid hormone (PTH) has not normalized at 1st post-operative visit, calcium and/or PTH is subsequently measured as necessary. Patient is defined to have a failed parathyroidectomy if hypercalcemia/hyperparathyroidism (defined as total blood calcium level > 10.5 mg/dL or 2.6 mmol/L, with/without elevated serum intact PTH > 65 pg/ml or 6.9 pmol/L) persists at or after the 6th postoperative month. [Time Frame: 6 months after PTx procedure]
- 4. Overall number of parathyroid glands identified

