 - a. Overall number of parathyroid glands identified (Experimental Group: Glands identified with naked eye + NIRAF; Control Group: Glands identified with naked eye) [Time Frame: Immediate. During PTx procedure.]
- 5. Number of parathyroid glands identified with NIRAF
 - a. Number of parathyroid glands identified with NIRAF, which was not seen with surgeon's naked eye [Time Frame: Immediate. During PTx procedure.]
- 6. Number of diseased parathyroid glands identified versus preoperatively localized glands
 - a. Number of diseased parathyroid glands identified intra-operatively versus glands localized preoperatively using sestamibi, CT or ultrasound [Time Frame: Preoperative to immediate during PTx procedure.]
- 7. Number of intra-operative parathyroid hormone (PTH) assays sent
 - a. Number of intra-operative parathyroid hormone assays sent during the procedure [Time Frame: Immediate. During PTx procedure.]
- 8. Duration taken to identify first parathyroid gland
 - a. Duration taken to identify 1st parathyroid gland in PTx procedure – timed from skin incision to finding PG. [Time Frame: Immediate. During PTx procedure.]
- 9. Duration taken to identify last parathyroid gland
 - a. Duration taken to identify last parathyroid gland in PTx procedure – timed from skin incision to finding the last PG. [Time Frame: Immediate. During PTx procedure.]
- 10. Duration of parathyroidectomy (PTx) procedure
 - a. Duration of PTx procedure – timed from skin incision until the surgeon notifies the anesthesia team to awaken the patient [Time Frame: Immediate. During PTx procedure.]
- 11. Duration taken for intraoperative parathyroid hormone (PTH) to normalize
 - a. Time taken for PTH to attain cure criteria or normalize - timed from skin incision until the PTH levels drops > 50% of its baseline value and/or PTH drops < 65 pg/ml or 6.9 pmol/L. [Time Frame: Immediate. During PTx procedure.]
- 12. Number of nights spent in the hospital after parathyroidectomy
 - a. Number of nights spent for postoperative recovery in the hospital after the surgical procedure. [Time Frame: 0-72 hours after PTx procedure.]
- 13. Number of 'false positive' tissues excised by surgeon
 - a. Number of tissues that were excised by surgeon assumed to be parathyroid tissue, but is later validated as nonparathyroid tissue (false positive) by histology [Time Frame: Immediate to 10 days after PTx procedure.]
- 14. Number of doctor visits/emergency department visits or hospital admissions

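### Lesser thyroid resections stay eligible and their time counts in procedure duration, and the frozen-section data item lacks the primary outcome's limit to suspected parathyroid tissue

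*Combined protocol and SAP*

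**What the plan says.** **Eligibility.** Section 4.0 admits "patients with primary hyperparathyroidism who will be undergoing parathyroid surgery" and, as a second group, adults having repeat surgery for persistent disease. The only exclusion touching the thyroid is "Patients with concurrent parathyroid and thyroid disease that require total thyroidectomy". Section 5.0 adds that "the study will aim to accrue all eligible patients who are going to the OR as part of their standard surgical procedure". It gives the surgeon the last word on eligibility, by reference to medical condition, and states no rule on smaller thyroid resections.

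**Time outcomes.** Section 2.0 defines outcome 10 as "Duration of PTx procedure – timed from skin incision until the surgeon notifies the anesthesia team to awaken the patient", with no deduction for other surgery. Outcomes 8, 9 and 11 (first gland, last gland, PTH normalisation) also start at incision. Outcome 12 counts recovery nights without separating causes.

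**Analysis.** Section 10.0 compares secondary outcomes with unadjusted two-group tests. Its one model is for the primary outcome, and the surgery-type term there separates only focused from bilateral operations.

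**Frozen sections.** The primary outcome in Section 2.0 counts specimens "sent for analysis during the procedure to confirm potential parathyroid tissue". Section 6.0, item (iii), compiles the "number of frozen section (or PTH aspirate) analysis performed" and then says that the compiled items will be compared between arms.

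**The concern.** Aim (ii) is surgical efficiency, and outcome 10 is its most direct measure. If some patients also have part of the thyroid removed, their recorded duration includes work that the device was never meant to shorten. Nothing in the plan records, stratifies on or adjusts for this, so it goes into the residual variation of the comparison.

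The frozen-section wording is a separate inconsistency. A section sent for a thyroid nodule lies outside the primary outcome as Section 2.0 defines it, but inside the data item as Section 6.0 words it. A data form built from Section 6.0 could produce a count that is not the primary outcome. The expected counts are small, so a few such specimens would show.

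**Working it through.** **The plan's own figure.** With a difference of 0.6, SD 0.8, two-sided 5% and 95% power (Section 10.0), n per group = 2 x (1.960 + 1.645)^2 x 0.8^2 / 0.6^2 = 46.2, so 47 as stated. Adding 15% gives 47 x 1.15 = 54.05, so 55 as stated (dividing by 0.85 gives 55.3, so 56). This point does not alter the sample size. I use 55 per arm because duration is known at the end of surgery.

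**A benchmark from the documents.** Section 10.0 gives preliminary means of 0.6 and 0.1 sections per patient, a difference of 0.5. Section 1.0 gives a wait of 20-30 min per sample, and Section 7.0 allows up to 5 min for the device.
- Waiting time avoided: 0.5 x 20 to 0.5 x 30 = 10-15 min.
- Net of device time: 5-10 min.

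This leaves out any gain from finding glands faster, which Section 2.0 also expects.

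**Assumptions, none of them in the documents.** Share f of patients with a concurrent lesser thyroid resection: 5-15%. Added time a: 45-60 min. SD s of duration otherwise: 30-40 min.

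**Formulas.**
- SD with thyroid surgery: s' = sqrt(s^2 + f(1-f)a^2).
- 95% chance half-width of the mean difference: 1.96 x SD x sqrt(2/55), with sqrt(2/55) = 0.1907.
- Half-width if affected patients are left out: 1.96 x s x sqrt(2/(55(1-f))).

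| f, a, s | f(1-f)a^2 | s' | No thyroid surgery | With it | Widening | Affected left out |
|---|---|---|---|---|---|---|
| 5%, 45, 40 | 96 | 41.2 | 14.95 | 15.39 | 0.44 | 15.34 |
| 10%, 60, 30 | 324 | 35.0 | 11.21 | 13.08 | 1.86 | 11.82 |
| 15%, 45, 40 | 258 | 43.1 | 14.95 | 16.11 | 1.16 | 16.22 |
| 15%, 60, 30 | 459 | 36.9 | 11.21 | 13.78 | 2.57 | 12.16 |

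Half-widths are in minutes. The first and last rows are the extremes of the assumed range. Variance rises by 6% (96/1600) to 51% (459/900). Leaving patients out gains almost nothing at 5%, helps when the added time is large relative to s, and can lose slightly when it is not (third row). Adjustment keeps everyone and, if the added time is roughly constant, brings the half-width back close to the column without thyroid surgery.

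**Which outcomes are affected.** Outcome 10 takes in the extra time in full. Outcome 12 may be affected. Outcomes 8, 9 and 11 are affected only if the thyroid work comes before their end points, and the documents do not say when it would.

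**Frozen sections.** At the preliminary means, 55 patients per arm give about 0.1 x 55 = 5.5 and 0.6 x 55 = 33 specimens. One thyroid specimen counted in error adds 1/55 = 0.018 to an arm's mean. How many there would be is unknown.

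**The case against.** The strongest reply is that the effect is small and speculative. No share of concurrent resections is given, the surgeon decides final eligibility, and if such cases are rare nothing changes. That stands, and it is why the size is given only as a range under assumptions.

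A reader might infer that chance imbalance in thyroid surgery moves the mean difference by about 4-8 min, as large as the saving itself. Taken alone, that component has a 95% range of 1.96 x a x sqrt(2f(1-f)/55), which is 3.7 min (5%, 45) to 8.0 min (15%, 60). But independent variances add, so this does not sit on top of the existing range. That range is already 11.2-15.0 min either way and exceeds the 5-10 min benchmark without any thyroid surgery. What the plan loses is the widening in the table.

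The table also concerns means. Section 10.0 reports medians and allows Wilcoxon's test according to the distribution of the data, and ranks are less sensitive to a long right tail. This also stands and makes the practical effect smaller.

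A reader might further infer that thyroid specimens contaminate the primary outcome. The Section 2.0 definition keeps them out, and item (iv) in Section 6.0 collects frozen-section and histology reports from which tissue could be classified. What remains is narrower: reports show what a tissue was, but nothing requires recording why it was sent. The surgeon knows the arm, so noting the target at the time is safer than sorting specimens afterwards.

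**Conclusion.** The point holds as a modest design improvement. Lesser thyroid resections are eligible, their time counts in full in outcome 10, and no planned analysis accounts for them. On the assumed 5-15% share, 45-60 added minutes and base SD of 30-40 min, the 95% chance range of the mean difference widens by about 0.4-2.6 min on a half-width of 11.2-15.0 min. If the share is near zero, so is the effect.

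The documents do not support a reading of systematic bias, because allocation is randomised and eligibility is the same in both arms. They do not show that thyroid surgery is the main limit on the duration comparison. The primary outcome is sound as defined; the fault is that the Section 6.0 data item does not match it.

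**What to change.** 1. Add one field, completed before allocation, for whether a thyroid resection is planned in the same operation.
2. In Section 10.0, pre-specify that outcome 10, and outcome 12, be analysed either adjusted for that field or restricted to patients without a planned resection, with the all-patient result also reported. Either way the comparison stays randomised, because the field is fixed before allocation. Adjustment is the safer default, since restriction does not always gain precision.
3. Do not restrict on resections decided during surgery, since that would select patients after allocation. Some of the noise will therefore remain.
4. In Section 6.0, item (iii), record the target of each frozen section or aspirate (suspected parathyroid or other) when it is sent, and count only the former for the primary outcome.

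The cost is one field per patient, one field per specimen and a sentence or two in the analysis plan. If the restricted analysis is chosen, a few patients are lost from outcomes 10 and 12 (on the assumed share, 0.05 x 110 = 5.5 to 0.15 x 110 = 16.5 of 110).
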